8.8 Study Drug Accountability

Commercially available Polvac™ will be purchased from Bencard AG (Switzerland). The study drug will be kept in a temperature-logged fridge (2-8 °C) with the pharma team at the Department of Dermatology. The pharma team will keep a log for received and used study medication.

The medical investigator will order drug from the pharma team, which will log study drug provision with date and time point (DD.MM.YYYY, HH:MM h). The time point for preparation of study drug is documented in the log with the pharma team and in the CRF (ILIT 400U and for SCIT 2000 U; directly syringed by the medical investigator).

8.9 Return or Destruction of Study Drug

At the end of the study, rest doses of Polvac™ are kept in the research lab in [name] for use in non-clinical research.

9. STUDY ASSESSMENTS

9.1 Study flow chart

The study flow chart is illustrated in **Figure 4**.

9.2 Assessments of outcomes

9.2.1 Assessment of primary outcome

FNA material of lymph node tissue at baseline and 6 hours after allergen injection (via ILIT or SCIT) will be evaluated for changes in lymph node cell populations and cell culture expression patterns.

Immunological changes (analysis of cell populations and cell cultures) in peripheral blood at baseline, after 2, 6 and 24 hours and at 7 and 28 days after allergen injection (via ILIT or SCIT).

9.2.1.1 Analysis of allergen-specific antibodies in serum by ImmunoCAP

The concentrations of IgE, IgG and IgG4 against grass-pollen allergens as well as tryptase are determined in serum using the ImmunoCAP system (ThermoFisher Scientific, Phadia, Waltham, US-MA) according to the manufacturer's instructions. This is a routine diagnostic method in our department.

9.2.1.3 Analysis of T-cell activation by flow cytometry

PBMCs are also analyzed by flow cytometry after allergen-restimulation in vitro. Briefly, the cells are typically cultured 18-20h in the presence of grass pollen allergens, the last 4-6 hours of the incubation, the compound brefeldin A is added to prevent the golgii apparatus to release newly produced proteins. Then, the cell are stained for with fluorescent antibodies to detect lymphocytes, lymphocyte activation surface proteins. The cell are then fixed, permeabilised and stained to detect intracellular transcription factors such as Foxp3, STAT-1 and STAT-3 and STAT-6 as well as intracellular cytokines such as IL-4, IL-10 and IFN-gamma. The exact cytokines may depend on the result from the above-mentioned ELISA

studies. The cells are acquired on a BD LSR-Fortessa Cell analyzer and the data analyzed using FlowJo LCC software.

[figure not shown]

Figure 4. Patient flow chart illustrating study visits with timing, interventions, and assessments for patients treated by ILIT or SCIT for grass pollen-mediated allergic rhinoconjunctivitis.

9.2.1.4 Multiparameter cellular analysis by mass cytometry (CyTOF)

PBMCs as well as lymph node cells are also analyzed by mass spectrum cytometry (45, 46) Again, cryotubes are thawed and cell immediately washed with complete medium. The cells are incubated with a viability dye washed extensively, and stained for a wide panel of extracellular antigens that will enable us to detect the phenotype of all possible leucocytes. After fixation and permeabilisation, the cells are patient-wise barcoded using the commercial Barcoding Kit (Fluidigm) and pooled before staining for intracellular antigens. Cell DNA is then stained using Cell-ID™ Intercalator-Ir (Fluidigm) overnight at 4°C, frozen at -80°C using a cryopreservation box, thawed, supplemented with Four Element Calibration Beads (Fluidigm) and acquired on a Helios™ mass cytometer. Files are concatenated, normalized, and debarcoded using the CyTOF software v6.7.1014. The data are analyzed by descriptive statistics as well as multivariate test methods with dimension reduction, e.g. PCA, t-SNE and UMAP (47).

9.2.2 Assessment of secondary outcomes

Differences in immunological response after injection of ILIT 400 U and SCIT 2000 U via two routes to demonstrate a possible route dependency.

9.2.3 Assessment of other outcomes of interest

None.

9.2.4 Assessment of safety outcomes

9.2.4.1 Adverse events

For reporting of adverse event information see 10.1.2.

To minimise the risk for AE the following precautions are carried out:

- The patients will receive an emergency set ("Allergie Notfallset") to take home in case of allergic side effects. The emergency set consists of two tablets of Xyzal® 5 mg and two tablets of Spiricort® 50 mg. Patients will be advised on when and how to use the emergency set.
- The patients will receive Fenistil gel 1% to use in case of local allergic side effects
- After the allergen injection the patients have to stay one hour at the allergy unit for observation of systemic allergic reactions as well as allergic skin reaction at the site of injection.
- The patients will be advised to call the medical investigators upon any delayed AEs or otherwise medical emergency if systemic allergic reactions (e.g. asthma).

9.2.4.2 Laboratory parameters

Before the allergen injection a pregnancy testing (if applicable) is performed. Pregnant participants are excluded from the clinical study.

9.2.4.3 Vital signs

A physical examination is done in a semi-structured way; several items are checked on a list in the CRF, and details can be entered if required.

The following vital signs will be assessed (e.g. heartbeat, lung auscultation and blood pressure).

9.2.5 Assessments in participants who prematurely stop the study

Most allergic events are resolved within a week, and we do not expect to have to follow patients for longer. If an AE is registered in a patients CRF this will be addressed by attending staff at the next visit. Patients will be able to contact staff by e-mail during the trial. If a patient should experience allergic symptoms severe enough to warrant hospitalization this will be recorded in the CRF.

Our injection in the framework of the study is not necessary for the routine therapy for the patients, therefore they don't need to be repeated in case of a withdrawal.

9.3 Procedures at each visit

9.3.1 Visit 1: Screening visit (20 minutes)

Completed until 02.02.2024 (-29 to 1 days before Visit 2)

- Interview with medical investigator
 - Medical history
 - Check of Inclusion/Exclusion criteria

- Physical examination
- Reading and signing of informed consent by participant and medical investigator

9.3.2 Visit 2 (120 minutes)

Completed until 03.02.2024 (at least 1 day after screening visit)

- Pregnancy testing (if applicable)
- Peak Flow before and 40 min after injection
- Venous blood collection before injection (5 ml serum and 25 ml EDTA)
- Injection of Polvac™ Grass+Rye (SCIT 2000U or ILIT 400 U)
- Immediately after injection
 - 1 h observation at the allergy unit of the University Hospital Zurich
 - Dispense of rescue medications
- 2, 6 or 24 hours after allergen injection the following parameters are obtained:
 - FNA of ILIT-treated inguinal lymph node or lymph node adjacent to SCIT injection
 - FNA of non-involved inguinal lymph node on the opposite side, which had not been treated (baseline measurement)
 - Venous blood collection (5 ml serum and 25 ml EDTA)

9.3.3 Visit 3 (30 minutes)

Completed until 04.02.2024 (2, 6 or 24 hours after SCIT/ILIT))

- Venous blood collection before injection (5 ml serum and 25 ml EDTA)
- FNA of ILIT-treated inguinal lymph node or lymph node adjacent to SCIT injection
- FNA of non-involved inguinal lymph node on the opposite side, which had not been treated (baseline measurement)

9.3.4 Visit 4 (10 minutes)

Completed until 24.03.2024 (7 days after injection)

- Venous blood collection (5 ml serum and 25 ml EDTA).

9.3.5 Visit 5 (20 minutes)

Completed until 31.03.2024 (28 days after injection)

- Venous blood collection (5 ml serum and 25 ml EDTA).
- Study termination

10. SAFETY

10.1 Drug studies

During the entire duration of the study, all adverse events (AE) and all serious adverse events (SAEs) are collected, fully investigated, and documented in source documents and case report forms (CRF).

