DSUR	Development safety update report
FNA	Fine needle aspiration
GCP	Good clinical practice
IB	Investigator's Brochure
Ho	Null hypothesis
HRA	Federal Act on Research involving Human Beings (in German: HFG, in French: LRH, in Italian: LRUM)
IEC	Independent Ethics Committee
IMP	Investigational Medicinal Product
IIT	Investigator-initiated Trial
ILIT	Intralymphatic immunotherapy
ITT	Intention to treat
PI	Principal Investigator
SCIT	Subcutaneous Immunotherapy
SDV	Source Data Verification
SmPc	Summary of Product Characteristics
SOP	Standard Operating Procedure
SPC	Summary of product characteristics
SUSAR	Suspected Unexpected Serious Adverse Reaction
TMF	Trial Master File
USZ	University Hospital Zurich

STUDY SCHEDULE

Table 1. Illustrating the study schedule with all interventions divided into the five visits. Patients will receive 6 SCIT injections as standard of care (not part of the study). 4-6 weeks later, the patients will be included in the clinical trials for assessment of immunological characteristics after a single ILIT or SCIT with subsequent fine needle aspiration (FNA), adverse event (AE) monitoring, and venous blood collection.

Visit / time point	1 Screening < 6 weeks of last SCIT	2 AIT	3 FNA	4 Follow-up	5 Follow up
		Day 0	Day 0-1	Day 7	Day 28
Required personnel	Nurse/MD	MD	MD	Nurse/MD	Nurse/MD
Informed consent	x				
Randomization	x				
Medical history	x				
Physical exam	x				
Incl./excl. criteria	x				
Blood samples		x	x	x	x
Pregnancy test		x			
AEs/Concomitant medication		x			x
Peakflow measurement		x*			
Injection: Study drug administration		x			
FNA (2x)			x**		
AE monitoring (1h observation at allergy unit after injection)		x			
Dispensing rescue medication		x			

* Peakflow measurement will be performed immediately before injection and 40 minutes after injection

** The FNA is performed 2, 6 or 24 hours after the Polvac™ ILIT or SCIT, and the injected (ILIT) or draining (SCIT) lymph node is used for FNA. For baseline reference, a contralateral lymph node is also aspirated.

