- The fine-needle aspiration (FNA) of the previously injected lymph node is a minimally invasive procedure and comparable to the ILIT procedure, hence, the potential AEs of ILIT injection and FNA are similar: infection and bleeding (hematoma). These problems are very rare, and antiseptic and ultrasound-guided procedures further minimizes the risk.

All SAE will be reported to the sponsor within 24 hours. SAEs will be followed up until one month after the end of the treatment period.

To minimize the risk of any allergic AEs, the patients will receive an emergency set ("Allergie Notfallset") for self-medication in case of side effects after the patient has left the study site. The emergency set consists of two tablets of Xyzal® 5 mg and two tablets of Spiricort® 50 mg (Appendix 003). Patients will be advised on when and how to use the emergency set. Furthermore after ILIT treatment the patients have to stay one hour at the allergy unit for observation.

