10.1.1 Definition and assessment of (serious) AEs and other safety related events

An **AE** is any untoward medical occurrence in a patient, or a clinical investigation participant administered a pharmaceutical product and which does not necessarily have a causal relationship with the study procedure. An AE can therefore be any unfavourable and unintended sign (including an abnormal laboratory finding), symptom, or disease temporally associated with the use of a medicinal (investigational) product, whether or not related to the medicinal (investigational) product. [ICH E6 1.2]

A **SAE** is classified as any untoward medical occurrence that:

- results in death,
- is life-threatening,
- requires in-patient hospitalization or prolongation of existing hospitalisation,
- results in persistent or significant disability/incapacity, or
- is a congenital anomaly/birth defect.

In addition, important medical events that may not be immediately life-threatening or result in death, or require hospitalisation, but may jeopardise the patient or may require intervention to prevent one of the other outcomes listed above should also usually be considered serious. [ICH E2A]

Examples of such events are intensive treatment in an emergency room or at home for allergic bronchospasm, blood dyscrasias or convulsions that do not result in hospitalisation, or development of drug dependency or drug abuse.

SAEs should be followed until resolution or stabilisation. Participants with ongoing SAEs at study termination (including safety visit) will be further followed up until recovery or until stabilisation of the disease after termination.

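### No scheduled AE or medication enquiry from about day 3–4 to day 27, although AEs are to be collected throughout and patients attend on day 7; SAE follow-up is stated in two ways

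*Combined protocol and SAP*

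**What the plan says.** Section 10.1 sets the scope: "During the entire duration of the study, all adverse events (AE) and all serious adverse events (SAEs) are collected". In Table 1 the row "AEs/Concomitant medication" is marked at Visit 2 (day 0) and Visit 5 (day 28) and is blank at Visits 3 and 4. A separate row for AE monitoring, which is the one-hour stay after injection, is marked at Visit 2 only.

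Section 9.3 lists the procedures visit by visit. Visit 2 includes "1 h observation at the allergy unit of the University Hospital Zurich" and the dispensing of rescue medication, but no AE or medication question. Visit 3 has a blood draw and two aspirations, the first being "FNA of ILIT-treated inguinal lymph node or lymph node adjacent to SCIT injection". Visit 4 (day 7) has a blood draw only. Visit 5 (day 28) has a blood draw and the end of the study.

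On SAEs, section 3.7 says "SAEs will be followed up until one month after the end of the treatment period". Section 10.1.1 says "SAEs should be followed until resolution or stabilisation", and adds that this continues beyond study termination for events still ongoing.

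**The concern.** A promise to collect every AE over four weeks needs points at which somebody asks. Here the marked points are the injection day and the last day. The day-7 visit between them has no AE or medication item in either the table or the list.

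Two things are at stake. The first is completeness and timeliness of safety data: an event a patient does not volunteer is learned of only at day 28, and the 24-hour SAE reporting duty in 10.1.2.1 starts to work only once staff know of the event. The second is interpretation of the immune readouts. Section 8.6 sends patients home with an antihistamine and prednisolone, and section 7.1 excludes other medication that interferes with the immune response. The plan thus regards such exposure as relevant, but schedules no question about it when the day-7 blood is drawn.

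The SAE follow-up statements are a separate inconsistency: an SAE still open about a month after the injection is treated differently by 3.7 and 10.1.1.

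**Working it through.** The plan gives no figure to reproduce here. The check compares the sections and counts days.

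**Step 1. Table 1 against section 9.3.**

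| Visit | Day | Table 1, AE/medication row | Section 9.3 list |
|---|---|---|---|
| 2 | 0 | marked | not listed (one-hour observation is) |
| 3 | 0–1 | blank | not listed |
| 4 | 7 | blank | not listed |
| 5 | 28 | marked | not listed |

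The column reading is supported by neighbouring rows: blood sampling has four marks, as expected for Visits 2–5, and FNA has one, as expected for Visit 3. Of the three visits after the injection visit, Table 1 schedules the enquiry at 1 and section 9.3 at 0.

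**Step 2. Other channels.**

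- Clinician assessment during the 60 minutes after injection (5.4).
- Observation for 30 minutes after FNA (8.2.1.2). FNA takes place at most 24 hours after injection, so by day 1.
- Home self-report: two days in 5.4, so to day 2; days 0–3 in the title of Appendix 006, so to day 3. That title names ILIT only, whereas 5.4 covers both routes.
- Calls (9.2.4.1) and e-mails (10.1.3) started by the patient, with no scheduled date.
- Section 10.1.3 has staff address, at the next visit, an AE already entered in the CRF. It does not describe asking about new ones.

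**Step 3. Length of the gap.** Days without scheduled enquiry = 27 − last day of home report.

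- Home report to day 2: 27 − 2 = 25 days (days 3–27).
- Home report to day 3: 27 − 3 = 24 days (days 4–27).

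The look-back needed at Visit 5 is 28 − 2 = 26 or 28 − 3 = 25 days. With a day-7 question, the look-back at Visit 4 is 7 − 2 = 5 or 7 − 3 = 4 days, and at Visit 5 it is 28 − 7 = 21 days.

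**Step 4. Which samples are exposed.** All FNA material and the 2–24 hour blood fall inside the home-report window. The day-28 blood coincides with a marked question in Table 1. The day-7 blood has neither: any medication affecting it would be asked about 21 days later. Vaccination is similar. Section 7.1 bars it for two weeks after injection, so to day 14. The day-7 sample lies inside that window, and the only later marked question comes 28 − 14 = 14 days after it closes.

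**Step 5. SAE follow-up.** Taking the treatment period to be the single injection on day 0, the limit in 3.7 falls at about day 28–31. Section 10.1.1 sets no calendar limit. Both cannot govern an SAE that is still open then.

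**The case against.** The best defence is that 10.1 says what is collected, not how often patients are asked. One question at day 28 covering the whole interval is compatible with it. That stands. A reader might infer that Table 1 flatly contradicts 10.1, or that staff never ask between day 0 and day 28. The documents do not support either reading. The 9.3 lists are not exhaustive: the Visit 1 list omits randomisation, which Table 1 marks. The CRF and questionnaires (Appendices 005 and 006) are named but not included, and may contain prompts. What is shown is that the schedule and the lists do not agree and that neither provides for a day-7 enquiry.

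It is also fair that early reactions are largely covered, including the first days after FNA, and that patients are told to report delayed events. A reader might go further and conclude that the lymph-node results are compromised. That does not follow, given their timing in Step 4. One reservation remains: 5.4 describes home reporting of reactions, and whether it also captures medication cannot be seen.

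A question at Visit 3 would add little for the 2-hour and 6-hour groups, where that visit falls on the injection day. On SAEs, 10.1.1 is the more detailed safety text, but nothing says that it overrides 3.7.

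**Conclusion.** The point holds as a gap in scheduled enquiry of 24 or 25 days, depending on which home-report window applies. Within it, AE and medication data depend on recall at day 28 or on the patient making contact. The sample mainly concerned is the day-7 blood. The size of any effect on a readout cannot be derived from the documents, and none is claimed. A day-7 question shortens the longest look-back only modestly, from 25–26 to 21 days. Its main gain is a medication and AE record made when the day-7 sample is taken.

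This rests on Table 1 being read correctly and on the unseen CRF not already prompting for these items at Visit 4. If it does, the remedy reduces to making the protocol say so. The disagreement between 3.7 and 10.1.1 on SAE follow-up does not depend on either assumption.

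**What to change.** - Mark AEs and concomitant medication at Visit 4 in Table 1, and add the line to 9.3.4. Include use of the emergency set and any vaccination since injection.
- Add the same line to 9.3.2 and 9.3.5 so that they match Table 1.
- Optionally, add to Visit 3 a line on medication taken before sampling. This is mainly useful for the 24-hour group.
- Align 5.4 with Appendix 006 on the home-report window, and state whether SCIT patients use the same questionnaire.
- Reconcile 3.7 and 10.1.1 so that one SAE follow-up rule applies. Which one is the sponsor's decision.

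The cost is one table mark, three lines and a few minutes at a visit patients already attend, plus the wording edits.

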10.1.1 Definition and assessment of (serious) AEs and other safety related events

An **AE** is any untoward medical occurrence in a patient, or a clinical investigation participant administered a pharmaceutical product and which does not necessarily have a causal relationship with the study procedure. An AE can therefore be any unfavourable and unintended sign (including an abnormal laboratory finding), symptom, or disease temporally associated with the use of a medicinal (investigational) product, whether or not related to the medicinal (investigational) product. [ICH E6 1.2]

A **SAE** is classified as any untoward medical occurrence that:

- results in death,
- is life-threatening,
- requires in-patient hospitalization or prolongation of existing hospitalisation,
- results in persistent or significant disability/incapacity, or
- is a congenital anomaly/birth defect.

In addition, important medical events that may not be immediately life-threatening or result in death, or require hospitalisation, but may jeopardise the patient or may require intervention to prevent one of the other outcomes listed above should also usually be considered serious. [ICH E2A]

Examples of such events are intensive treatment in an emergency room or at home for allergic bronchospasm, blood dyscrasias or convulsions that do not result in hospitalisation, or development of drug dependency or drug abuse.

SAEs should be followed until resolution or stabilisation. Participants with ongoing SAEs at study termination (including safety visit) will be further followed up until recovery or until stabilisation of the disease after termination.

10.1.1.1 Assessment of Causality

Investigators and Sponsor make a causality assessment of the event to the study drug, based on the criteria listed in the ICH E2A guidelines:

Relationship	Description
Unrelated	This category is applicable to those AEs which, after careful medical consideration at the time of evaluation, are judged to be clearly and incontrovertibly due to extraneous causes (disease, environment, etc) and do not meet the criteria for study medication relationship listed under remote, possible, or probable.
Unlikely	In general, this category is applicable to those AEs which, after careful medical consideration at the time they are evaluated, are judged to be remotely related to the test study medication. An AE may be considered remote if, or when, for example: (i) it does not follow a reasonable temporal sequence from administration; (ii) it could readily have been produced by the patient's clinical state, environmental or toxic factors, or other modes of therapy administered to the patient; (iii) it does not follow a known response pattern to the suspected study medication.
Plausible	(Must have the first 2 criteria): This category is applicable to those AEs which, after careful medical consideration at the time they are evaluated, the connection with the test study medication administration appears unlikely but cannot be ruled out with certainty. An AE may be considered plausible if, or when: (i) it follows a reasonable temporal sequence from administration; (ii) it could readily have been produced by the patient's clinical state, environmental or toxic factors, or other modes of therapy administered to the patient; (iii) it follows a known response pattern to the suspected study medication.
Probable	(Must have the first 3 criteria): This category is applicable to those AEs, which, after careful medical consideration at the time they are evaluated, the connection with the test study medication administration appears to, with a high degree of certainty, be related to the test study medication. An AE may be considered probable if: (i) it follows a reasonable temporal sequence from administration; (ii) it could not be reasonably explained by the known characteristics of the patient's clinical state, environmental or toxic factors, or other modes of therapy administered to the patient; (iii) it disappears or decreases on cessation or reduction in dose. There are important exceptions when an AE does not disappear upon discontinuation of the study medication, yet study medication-relatedness exists, e.g. bone marrow depression, fixed study medication eruptions, and tardive dyskinesias; (iv) it follows a known response pattern to the suspected study medication; (v) it reappears upon rechallenge.
Not assessable	When not possible to assign the event to any of the criteria mentioned above.

